Development and internal validation of models involving vital signs to predict troponin level and myocardial injury after noncardiac surgery: a single-centre retrospective cohort study

Introduction

The incidence of myocardial injury after noncardiac surgery (MINS) is approximately 12-15% and is associated with an increased risk of 30-day mortality (1), 1-year mortality (2), and 2-year major vascular events (3). Since more than 90% of patients with MINS are asymptomatic, routine troponin monitoring is required for detection (4). The postoperative days 0, 1, and 2 accounts for approximately 40%, 40%, and 10% of MINS, respectively (4). Presently, the Canadian Cardiovascular Society (CCS) perioperative guidelines recommend patients identified to be at risk according to the Revised Cardiac Risk Index (RCRI) and BNP/NT-proB-type Natriuretic Peptide (NT-proBNP) receive daily postoperative troponin monitoring for three days to identify MINS events (5). European and American societies have similar recommendations for troponin monitoring to detect MINS (6).

Current risk stratification models have multiple limitations (4). Most importantly, they predict an elevated risk over the postoperative period but cannot pinpoint when MINS may happen in the postoperative course given the patients' changing condition. Moreover, prescription of troponin monitoring is not universal (7), infrequent and inconsistent troponin monitoring may lead to delayed detection and management, and the rise of troponin is delayed by 3-4 hours from the time of injury (4).

Retrospective cohort studies show association amongst intraoperative and postoperative derangements in vital signs and MINS (4). Vital signs are routinely available within the electronic medical record, and may serve as objective predictors (i.e. as opposed to free text and disease names that have higher risks of misclassification and errors). Using both traditional longitudinal analysis techniques and novel methods in machine learning, we will investigate whether intraoperative and postoperative vital signs can enhance MINS surveillance by providing temporal prediction of MINS events.

Table 1. Preoperative factors studied in literature associated with MINS and/or major myocardial complication and mortality

Variable	References
Age	Goldman 1977 (8), Lee 1999 (9), Kheterpal 2009 (10), Botto 2014 (11), House 2016 (12)
Congestive heart failure	Lee 1999, Botto 2014
Coronary artery disease	Lee 1999, Kheterpal 2009, Botto 2014

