2. To develop and internally validate a model that uses the duration and degree of intraoperative and postoperative hypotension to predict daily probability of MINS or death (binary outcome, according to the 2021 American Heart Association (AHA) definitions (6) from postoperative days zero to two.
3. To evaluate how different definitions of hypotension affect the primary and secondary models above, and analyze the intraoperative and postoperative hypotension separately to determine whether intraoperative or postoperative hypotension alone are sufficient for prediction.
4. To explore whether other intraoperative and postoperative vital sign information (heart rate, oxygen saturation, and end-tidal carbon dioxide derangements at various definitions) add predictive value to the primary and secondary models above.
5. To use machine learning methods to perform exploratory analysis to determine 1) optimal methods for imputation for time series data; 2) visualization of time series data in the setting of prediction; 3) development and internal validation of machine learning models to use the time series data to predict troponin levels; and 4) to determine how many hours earlier than a binary MINS diagnosis were vital signs able

to predict a MINS diagnosis (as determined by when in the time series prior to MINS diagnosis that the model achieved various thresholds of predicted probability).

Methods

This is a single-center, retrospective cohort study on the development and internal validation of a prediction model.

Population

This study will include patients aged 45 years and older undergoing inpatient noncardiac surgery, who had MINS protocol ordered for postoperative high sensitivity troponin monitoring based on the CCS guidelines (5) from January 2020 to June 2021 (estimated sample size of 750, event rate of ~75).

Patients will be excluded if they do not have intraoperative and postoperative vital signs, or any postoperative troponin measurements. Patients who underwent repeat surgery or were readmitted within the first 72 hours postoperatively will be excluded, since patients who are discharged and readmitted will not have vital measurements as outpatients. If a patient had multiple admissions where the MINS protocol was ordered, only the first inpatient admission will be included. Patients who had positive troponin on postoperative day 4 will be excluded, since vital signs are only included up to postoperative day 3 for consistency.

Data sources

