Following research ethics board approval, data will be extracted from Cerner Surginet Anesthesia (intraoperative electronic records) and Cerner PowerChart (preoperative and postoperative electronic records). The extracted data will consist of cohort characteristics (patient, anesthetic, surgical variables relevant to MINS (see Data Dictionary below), and patient vital signs with time stamps up to postoperative day 3. The time series time stamps will be transposed to have the start of surgery as 00:00, Jan 1, 2020. A manual chart review will also be performed to extract data not automatically retrieved from Cerner and Surginet (e.g. diagnoses of morbidities). We will extract relevant preoperative comorbidities, including RCRI and Charlson Comorbidity Index categories that are available to the Cerner team via CIHI with no date limit to obtain all preoperative comorbidities (please see Appendix). The Cerner, Surginet, and chart review data will then be linked by de-identified study ID and full surgery date.

Duration of data collection

Preoperative laboratory values are collected within 30 days before surgery. Preoperative vitals are collected within 24 hours before surgery. The total duration of subsequent data collection will be from the time of surgery up to postoperative day 3 (since the MINS protocol monitors for 3 days) or hospital discharge or death, whichever occurs first. Since 90% of MINS happen between postoperative days zero and two (4) and the frequency of monitoring would likely decrease by postoperative day 3, we will model troponin from postoperative day 0 to postoperative day 2 for the primary analysis to balance utility of the temporal model and prediction data quality.

Outcome

In the primary model, we will model high-sensitivity troponin (hsTnT) level as a continuous outcome, such that the model will remain useful if the troponin threshold definitions for MINS evolve.

In the secondary model, we will use the American Heart Association (AHA) definitions (6) for MINS, briefly:

1. Postoperative hsTnT 20 to <65 ng/L with an absolute increase of ≥ 5 ng/L amongst any postoperative troponins, or ≥ 65 ng/L, “attributable to a presumed ischemic mechanism (ie, supply-demand mismatch or atherothrombosis) in the absence of an overt precipitating nonischemic cause (eg, pulmonary embolism)”. The timestamp for laboratory diagnosis will be set at the time that the sample of elevated troponin was drawn.

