 - a. Nonischemic causes that may be temporally associated (around the time prior to troponin elevation) were individually chart reviewed, and include PE/DVT, sepsis, rapid atrial fibrillation, cardioversion within 24 hours as per the VISION trial (33). Rapid atrial fibrillation will be established as the presence of atrial fibrillation on ECG with a ventricular rate >100 bpm. Sepsis will be defined as the presence of infection and a systemic inflammatory response (SIRS) and per the Third International Consensus Definitions for Sepsis and Septic Shock (Sepsis-3). SIRS requires 2 or more of the following features: core temperature > 38 C or < 36 C; heart rate > 90 beats per minute; respiratory rate > 20 breaths per minute; WBC count $> 12 \times 10^9/L$ or $< 4 \times 10^9/L$ (34).
2. In patients with abnormal baseline troponin values (>14 ng/L) that is considered chronic and stable, postoperative myocardial injury is considered acute if there is postoperatively a $\geq 20\%$ rise in high-sensitivity cTnT, or an absolute increase in high-sensitivity cTnT of ≥ 14 ng/L above preoperative values. If a patient was diagnosed as having preoperative acute myocardial infarction, there must be a decrease in preoperative hsTnT to be considered chronic elevation for this rule to apply. Manual physician adjudication will be performed as a double check.

Note that MINS includes myocardial infarction in the AHA definitions. If a patient died before MINS diagnosis within 3 days postoperatively, this will be considered an event - i.e. the outcome is specifically MINS or death, to avoid competing risk bias due to death. However, we anticipate death within 3 days after surgery to be very rare.

Only the first positive MINS event is included, and hemodynamic data will be truncated up to that point. The MINS “diagnosis time” of MINS vs. no MINS is the first troponin in the serial troponin that fits the MINS criteria, with the start time defined as since the start of the surgery.

The exploratory modeling objectives will model both troponin level and MINS definitions.

Vital sign candidate features (predictors)

- Vital signs time series (SBP, MAP, DBP, HR, SpO2): taken from Surginet (intraoperative) and Cerner (preoperatively on the day of surgery, and postoperative)
 - These will be modeled using time series data from 1) intraoperative only, 2) postoperative only, and 3) both intraoperative and postoperative periods, using the following approaches:

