We will evaluate unsupervised machine learning techniques to describe and cluster patterns of time series data. This would help with classification and prediction, visualization, and interpretability. Then, we will use supervised machine learning techniques to evaluate what patterns in the time series drove predictions in the models, and whether we can determine how much sooner the machine learning models were able to predict myocardial injury events prior to laboratory detection. The visualization codes will be wrapped into a Python package for visualization.

Aim 3:

To determine whether the predictive performance can be improved by using machine learning over traditional models, we will develop and internally validate machine learning models (including boosted trees and neural networks) to predict outcomes as described above, using time series or summary vital sign variables. The modeling is limited by the small sample size and class imbalance, and specific techniques will be explored including temporal-based resampling in the derivation set, one-class learners, and autoencoders.

Participant Confidentiality and Privacy

The dataset contains de-identified perioperative patients. Only those listed on this protocol will have access to the de-identified dataset for the duration of this project. The dataset created for the study will be saved in a password-protected file after the completion of the study or, if applicable, after the publication of study results (whichever happens later). At the end of 5 years, the data will be deleted permanently in accordance to UBC IT policy.

Potential for Risk and/or Harm

This study involves the secondary use of existing de-identified data, and no additional data will be collected. There is no foreseeable risk of the possible disclosure of any identifiable data because the current research will involve de-identified secondary data only.

Report of Findings

The findings from this research will be presented to the St. Paul's Hospital Anesthesia Department through a grand rounds presentation. In addition, there may be the opportunity to present this at an anesthesiology conference and produce a peer-reviewed publication from this data.

Data Dictionary

Source: Surginet extraction

Variable name	Legend	Reason for request
IDN	ID (deidentified)	To deidentify patients in the dataset

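### The lead-time analysis counts hours from threshold crossing to diagnosis in MINS cases only and is tied to no false-alarm rate, so chance crossings can be reported as early warning

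*Combined protocol and SAP*

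**What the plan says.** Objectives, item 5 is labelled exploratory. Its fourth part sets out "to determine how many hours earlier than a binary MINS diagnosis were vital signs able" to predict that diagnosis, and gives the rule: "as determined by when in the time series prior to MINS diagnosis that the model achieved various thresholds of predicted probability". Approach II, Aim 2 returns to the question of "how much sooner the machine learning models were able to predict myocardial injury events prior to laboratory detection". Neither place names a threshold, an alarm-rate or specificity limit, a comparison with MINS-free patients, or a rule for cases that never cross.

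Three further statements fix the window in which a crossing can occur:

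- Under Outcome, time runs "with the start time defined as since the start of the surgery", and a case's haemodynamic series stops at its first MINS event.
- Also under Outcome: "The timestamp for laboratory diagnosis will be set at the time that the sample of elevated troponin was drawn".
- The Introduction describes at-risk patients who "receive daily postoperative troponin monitoring for three days to identify MINS events".

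Model evaluation, under Approach I, plans ROC curves with AUC, calibration and decision curve analysis for the binary models. Precision-recall curves are to be considered.

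**The concern.** Only a patient with a diagnosis has a time from crossing to diagnosis, so the quantity in Objective 5(4) exists only for MINS cases. MINS-free patients who cross the same threshold leave no trace in it. A crossing that occurs by chance hours before a case's diagnosis counts the same as one caused by evolving injury.

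Two things then largely determine the reported hours, whether or not the score carries information. One is how long cases wait from surgery to the diagnostic draw, which includes the wait for the next scheduled sample. The other is how low the threshold is set. The Introduction motivates the study by the inability of current tools to time MINS, so hours gained over the laboratory is a result that readers would quote. Without a false-alarm anchor it cannot separate usable warning from chance.

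**Working it through.** The plan states no lead time, threshold or alarm rate, so there is no figure to reproduce. The check asks what the rule returns for a score with no information.

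**1. The cap on lead.** The Introduction states: "The postoperative days 0, 1, and 2 accounts for approximately 40%, 40%, and 10% of MINS, respectively". Assume a 3 h operation, uniform timing within each day and the remaining 10% on day 3. Day 0 then spans 3–27 h from the start of surgery and day 1 spans 27–51 h.

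- Median: 27 + (50 − 40)/40 × 24 = 33 h
- Lower quartile: 3 + 25/40 × 24 = 18 h
- Upper quartile: 27 + (75 − 40)/40 × 24 = 48 h

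A typical case therefore has more than a day in which any crossing counts as early prediction. Lead cannot exceed this time.

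**2. An uninformative score.** The Population section gives "estimated sample size of 750, event rate of ~75", so mean risk is 75/750 = 10%. The score is logit p(t) = μ + σz(t), with z(t) = 0.9 z(t−1) + √(1 − 0.81) ε(t). It is updated hourly and is independent of outcome, and μ is set so that the mean of p is 0.10. Assumed values are σ = 0.7 and diagnosis uniform at 6–48 h. Lead is diagnosis time minus first crossing, among cases that cross before diagnosis. MINS-free patients are followed for 72 h.

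| Threshold | Cases flagged | Median lead if flagged | MINS-free ever crossing in 72 h |
|---|---|---|---|
| 10% | 88% | about 22–23 h | 99.6% |
| 15% | 65% | 20 h | 93% |
| 20% | 42% | 18 h | 74% |
| 30% | 13% | 16 h | 28% |

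In the planned cohort, the 20% threshold would flag about 0.42 × 75 = 31.5 cases and 0.74 × 675 = 499.5 MINS-free patients. The share of flagged patients who are cases is 31.5/531 = 5.9%. It falls below the 10% base rate because cases are cut at diagnosis while MINS-free patients are followed longer. The planned measure would report the 18 h and none of the rest.

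**3. Sensitivity to assumptions.**

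- *Centring.* With the median rather than the mean risk at 10%, the shares of cases flagged become about 93/77/55/20%.
- *Spread.* At σ = 0.35, 7% of cases cross 20% and about 0.1% cross 30%. At σ = 0.2, essentially none cross 20%. At σ = 0.5–0.7, at most 0.5% cross 50%. A constant prediction of 10% never crosses a higher threshold.
- *Timing.* With the day split from step 1, σ of 0.5 or 1.0, hourly correlation 0, 0.9 or 1, and updates every 1 or 4 h, median lead was about 22–35 h wherever an appreciable number of cases crossed.

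**4. Is a false-alarm cap enough?** Set the threshold so that 10% or 20% of MINS-free patients alarm within 72 h (σ = 0.7). The uninformative score then flags about 4% or 9% of cases. Counting unflagged cases as zero, mean lead is 0.7 or 1.5 h and the median is 0. Among flagged cases alone the median lead is still about 16 h, so the cap by itself does not remove the artefact. The 4% against 10% comparison is also unequal, because the two groups are followed for different lengths of time.

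**5. Matched pseudo-diagnosis times.** Give MINS-free patients times drawn from the case distribution. In the day-split runs (hourly, correlation 0.9, σ = 1.0, threshold at a 10% alarm rate over 72 h), cases and matched MINS-free patients were both flagged at 5.2%, with median leads of 22.1 h in each. Equal flag rates and equal leads show directly that there is no signal.

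**The case against.** The strongest reply is that the plan does assess false positives. AUC, calibration and decision curves across thresholds are planned, Outcome says the exploratory models will cover the MINS definitions, and Aim 3 includes internal validation. An uninformative model would show an AUC near 0.5. This stands: a reader of the full report would see that such a model is useless overall, and it would be wrong to infer that the plan ignores false alarms. What it does not cover is the lead-time result itself. Those checks are written under Approach I and are linked neither to crossing time nor to its thresholds. A model with modest AUC could still be reported as predicting MINS most of a day early.

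Three stronger readings are tempting, and the documents do not support them:

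- *Any noise model will show a long lead.* This depends on the spread of the score and on the threshold (step 3), and the documents give neither.
- *Lead grows without limit as the threshold falls.* It is capped, because the series starts at surgery and ends at diagnosis.
- *The plan fixes a first-crossing measure and will leave MINS-free patients out of the report.* First crossing is the natural reading, but the text does not say first or sustained. Nor does it say that MINS-free results will be withheld. What can be said is that the stated quantity cannot be computed in them and no companion quantity is planned.

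It is also fair that this is one part of an exploratory objective.

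**Conclusion.** The concern holds in a bounded form. As written, the rule can report chance crossings as hours of early warning, and nothing attached to it would show this. Under the stated assumptions, an uninformative score yields median leads of about 16 to 23 h at thresholds of 10–30% in the 13–88% of cases it flags, while 28–99.6% of MINS-free patients cross the same thresholds over 72 h. The hours and shares rest on the assumed spread, correlation and diagnosis timing, and a score that stays below the threshold gives no lead. The plan does not exclude the low thresholds at which the problem is largest.

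No primary or secondary result is affected. The change is worth making because temporal prediction is the study's stated motivation and the data needed are already in hand.

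**What to change.** Add to Approach II, Aim 2:

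1. Use held-out (cross-validated) predictions only, and state whether a crossing means first or sustained.
2. Give each MINS-free patient a pseudo-diagnosis time drawn from the case distribution of diagnosis times, within that patient's observed follow-up, and cut the series there.
3. Set thresholds at fixed false-alarm rates in these patients over that matched follow-up, for example 10% and 20%.
4. At each threshold report the share of cases flagged before diagnosis, and the lead time with unflagged cases counted as zero. Give the mean and distribution, since the median is zero whenever fewer than half are flagged.
5. Show the same quantities for the matched MINS-free patients and for a reference model without vital signs. The reference matters because a score that is constant within a patient crosses at time zero, so it collects the longest lead of all (about 33 h in the day-split runs).

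An uninformative score should then flag about the same share of cases as the chosen false-alarm rate, with equal leads in the two groups.

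The cost is a little more code and a short paragraph in an exploratory aim, with no new data. The downside is that reported lead times will be shorter.

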***A priori* features in the primary model**

This *a priori* list of predictors will be used for the primary modeling in Objective 1: duration hypotension (summarized as a percentage of duration of MAP<75 mmHg in the duration of time modeled, e.g. postoperative day 0, 1, and 2), age, sex, emergency surgery, RCRI, and postoperative GFR, as well as the postoperative day and the interaction between postoperative day and % duration MAP<75mmHg as detailed below.

Statistical analysis

Missing data

We will exclude patients with no intraoperative or postoperative vital signs and no troponin measurements from the cohort. Complete case analysis will be performed for vital sign features, with each complete case defined as a patient with ≥ 1 vital sign measurement(s) and ≥ 1 troponin measurement(s). Since the frequencies of measurements are different, missing vital signs are not considered missing values for inclusion/exclusion purposes as long as patients meet the complete case criteria. No imputation will be performed for vital sign data.

For features that are not vital signs (e.g. age, sex), we anticipate minimal missing data (as these variables are routinely collected), and assume missing at random. Due to the longitudinal data structure with correlated observations, we opted for a simpler method of imputation for the primary analysis. For features missing $< 1\%$, complete case analysis will be

performed; between 1-<10%, multiple imputation; above 10%, the feature would be excluded from the model and the reason for missing data will be investigated.

Data quality

The data quality of the CIHI vs. chart review results of the comorbidity information will be assessed by Pearson correlation, with chart review as the gold standard.

Cohort characteristics

Continuous data will be presented in mean (SD) if normal, and median (IQR) if non-normally distributed. Categorical data will be presented as frequency (%). The following characteristics will be presented as overall group, and stratified by MINS vs. no MINS:

- Age
- Gender
- American Society of Anesthesiologists' physical status classification (ASA)
- Type of anesthesia (general, neuraxial, peripheral, and/or sedation)
- RCRI score and categories: pre-existing TIA/CVA, insulin dependent diabetes, serum creatinine >177 mmol/L, coronary artery disease, congestive heart failure, and high risk surgery including intrathoracic, intraabdominal or suprainguinal vascular surgery

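### Requiring a postoperative troponin for entry removes deaths before the first sample, which the secondary MINS-or-death model is defined to count as events

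*Combined protocol and SAP*

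**What the plan says.** Three parts of the plan bear on this point.

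- **Entry (Population).** "Patients will be excluded if they do not have intraoperative and postoperative vital signs, or any postoperative troponin measurements". No exception is made for patients who died.
- **Complete cases (Statistical analysis, Missing data).** "We will exclude patients with no intraoperative or postoperative vital signs and no troponin measurements from the cohort". Vital-sign features are then analysed in complete cases, "with each complete case defined as a patient with ≥ 1 vital sign measurement(s) and ≥ 1 troponin measurement(s". Again no exception is made for death.
- **Outcome.** Objective 2 is a model "to predict daily probability of MINS or death" over postoperative days 0 to 2. The Outcome section says "If a patient died before MINS diagnosis within 3 days postoperatively, this will be considered an event", and gives the reason: "the outcome is specifically MINS or death, to avoid competing risk bias due to death". A death needs no troponin to count. The section adds: "However, we anticipate death within 3 days after surgery to be very rare".

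The expected scale is given in Population as "estimated sample size of 750, event rate of ~75".

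**The concern.** The cohort is defined by an order: patients for whom the MINS troponin protocol was requested. Whether a sample was later drawn is known only after surgery. Making it a condition of entry means that a patient must survive to the first draw to be studied.

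This suits the primary model, whose outcome is a troponin value. It does not suit the secondary model, where death alone settles the outcome. Death before any sample is the plainest case of death preventing MINS from being observed, which is the problem the composite was introduced to handle. Under the rules as written, those deaths are left out of both the events and the denominator of the model meant to include them.

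**Working it through.** **Step 1. Compare the rules for patients who die within 3 days without a prior MINS diagnosis.**

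| Patient | Outcome rule | Entry and complete-case rules | Result |
|---|---|---|---|
| Dies after one or more non-diagnostic postoperative troponins | Event | Troponin requirement met | Counted |
| Dies before any postoperative troponin | Event | Fails the Population rule | Lost |

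Primary Modeling describes troponin monitoring as daily, so an interval before the first sample exists. Only the second row is affected.

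**Step 2. Reproduce the plan's figures.** The 750 patients and about 75 events are given as estimates without a formula, so they cannot be derived. They imply 75/750 = 10.0% and, with the 8-variable cap in the parameter-count section, 75/8 = 9.4 events per variable.

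**Step 3. Size of the loss.** Lost events = 750 × m × f, where m is 3-day mortality and f is the share of those deaths before any postoperative sample. The documents give neither, so both are assumptions: m from 0.2% to 1%, f from one third to one half.

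| m | f | Lost events | Relative to 75 |
|---|---|---|---|
| 0.2% | 1/3 | 750 × 0.002 × 1/3 = 0.5 | 0.7% |
| 0.2% | 1/2 | 750 × 0.002 × 1/2 = 0.75 | 1.0% |
| 1% | 1/3 | 750 × 0.01 × 1/3 = 2.5 | 3.3% |
| 1% | 1/2 | 750 × 0.01 × 1/2 = 3.75 | 5.0% |

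Restoring them moves the event rate from 10.0% to between 75.5/750.5 = 10.06% and 78.75/753.75 = 10.45%, and events per variable from 9.4 to between 75.5/8 = 9.4 and 78.75/8 = 9.8. A wider range (m 0.1% to 1%, f 25% to 100%) gives 0.2 to 7.5 events. Its upper end needs 1% mortality with every death before sampling, which sits poorly with the plan's expectation of rarity.

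**Step 4. Would changing only the entry rule be enough?** No. Three other rules could remove the same patients.

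- The complete-case definition under Missing data separately requires a troponin.
- The Population sentence also asks for postoperative vital signs, which a very early death may lack.
- Postoperative GFR is an a priori predictor in both models. If only these patients lacked it, missingness would be 0.5/750 = 0.07% to 3.75/750 = 0.5%. That is below the 1% at which the plan moves from complete-case analysis to multiple imputation, so they would be dropped again.

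**The case against.** The strongest reply is that at least one troponin is a reasonable entry requirement: MINS cannot be determined without one, and troponin is the primary outcome. That stands for the primary model and for unsampled survivors. It does not cover a patient whose secondary outcome is already settled by death.

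A second reply is that admitting unsampled patients only if they died makes inclusion depend on the outcome. This is a fair point about cost. As an illustration, take 750 sampled patients with 75 events, 2 unsampled deaths, and 50 unsampled survivors with MINS at the sampled 10% rate (5 events). The event rate in all 802 is 82/802 = 10.22%. Keeping the deaths gives 77/752 = 10.24%; dropping them gives 75/750 = 10.00%. The comparison depends on the survivors' rate: if none of the 50 had MINS, the overall rate would be 77/802 = 9.60%, and dropping the deaths would happen to lie nearer. The survivors are excluded under either option, however, and the differences are fractions of a percentage point. The objection calls for both counts to be reported with a sensitivity analysis; it does not justify discarding known events.

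Two stronger readings are tempting, and the documents support neither.

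- A reader might infer that the composite misses most of the deaths it was meant to capture. Deaths after a non-diagnostic sample remain events, and under the assumptions above those are half to two thirds of early deaths.
- A reader might infer that the lost patients had the most severe hypotension, so that the hypotension effect is biased. That is plausible, but no section describes blood pressure in early deaths or unsampled patients.

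**Conclusion.** The inconsistency is real, and nothing in the plan resolves it: a death within 3 days before the first postoperative troponin is both an event and an exclusion. It affects only the secondary binary model, and only that subset of early deaths.

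The likely size is small, about 0.5 to 4 events against roughly 75. This rests on assumed mortality and timing, and on treating the planned 750 as the sampled cohort. No effect on discrimination, calibration or coefficients has been shown, and the documents do not allow one to be calculated. This is a minor correction that brings the cohort into line with the stated purpose of the composite.

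**What to change.** For the binary model only:

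1. In Population and in Missing data, apply the troponin requirement only to patients alive at 72 hours or discharged. Count deaths within 3 days without a postoperative troponin as events on the day of death.
2. For these deaths, waive the postoperative vital-sign requirement where intraoperative vital signs exist.
3. For these deaths, impute missing postoperative GFR or use the preoperative value, which the data dictionary already lists, so that the complete-case rule for under 1% missingness does not remove them.
4. Report how many such deaths there are and how many unsampled survivors are excluded. Give the result without these deaths as a sensitivity analysis.

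While editing, align the two statements of the exclusion. Missing data joins its conditions differently from Population and does not say that the troponin must be postoperative, so a patient with only a preoperative value could be read as a complete case.

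**Cost.** The primary and secondary models will have slightly different cohorts, and the event rate is pulled up a little because unsampled survivors stay excluded. The data dictionary lists in-hospital mortality only as yes or no, so the time of death must be obtained; the planned truncation of the series at death needs it anyway. The continuous troponin model does not change.
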